## **Study Timeline**

- Estimated Duration: 1 visit and subsequent visit to continue the root canal treatment.
- Key Milestones:
  - Participant recruitment (2 months).
  - Data analysis and reporting (3 months).

#### **Ethical Considerations**

- The study has been reviewed and approved by the Institutional Review Board (IRB) of Misr International University. (IRB Number: MIU-IRB-2425-008)
- Participant confidentiality will be maintained in compliance with ethical guidelines.

# **Funding and Conflict of Interest**

- No external funding has been received for this study.
- The researchers declare no conflicts of interest.

Title: Diagnostic Accuracy of Artificial Intelligence, CBCT, and Clinical Examination in Detecting Number of Root Canals in Conventional and Retreated Maxillary and Mandibular Molars

NCT Number: “Pending”

Date: 29/10/2024

Statistical Analysis

Qualitative data were presented as frequencies and percentages. Friedman's test was used to compare between number of canals detected by the three methods. Kappastatistic was used to assess agreement between the threemethods. Kappa values ranging from 0.6 to 0.8 indicate good agreement while values ranging from 0.8 to 0.99 indicate very good agreement. Numerical data were explored for normality by checking the distribution of data and using tests of normality (Kolmogorov-Smirnov and Shapiro-Wilk tests). All data showed normal (parametric) distribution except for length of canal division from the apex and percentage of canal unity data which showed non-normal (non-parametric) distribution. Data were presented as mean, standard deviation (SD), median and range values. For parametric data, Student's t-test was used to compare between correctly and incorrectly diagnosedcases. For non-parametric data, MannWhitney U was used to compare between correctly and incorrectly diagnosed cases. Binary logistic regression model was constructed using diagnosis (Correct/Incorrect) as the dependent variable. Treatment, molar type, inter-orifice distance, percentage of canal unity and Vertucci classification were the independent variables. The significance level was set at $P \leq 0.05$. Statistical analysis was performed with IBM SPSS Statistics for Windows, Version 23.0. Armonk, NY: IBM Corp. ROC (Receiver Operating Characteristic) curve was constructed to determine the diagnostic accuracy measures of AI in relation to CBCT. Comparison between areas under the ROC curve (AUC) were performed using z-test. ROC curve analysis was performed with MedCalc® Statistical Software version 19.5.1 (MedCalc Software Ltd, Ostend, Belgium; <https://www.medcalc.org>; 2020)

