# **Study Objectives and Hypotheses**

• **Objective**: To evaluate and compare the accuracy of AI, CBCT, and clinical examination in detecting the number of root canals in maxillary and mandibular molars.

• **Hypothesis**: AI will demonstrate superior diagnostic accuracy compared to CBCT and clinical examination.

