#### **Statistical Analysis Plan**

- Descriptive analysis of frequencies and percentages.
- Friedman's test for comparison between methods.
- Kappa statistics for agreement between methods.
- ROC curve analysis to determine diagnostic accuracy measures (AUC comparison).

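### The hypothesis is that AI is more accurate, but no planned test compares the methods' accuracy against a named, independent reference

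*SAP*

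**What the plan says.** Under Study Objectives and Hypotheses the protocol states: "AI will demonstrate superior diagnostic accuracy compared to CBCT and clinical examination". The analyses offered for this are as follows.

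- **Friedman.** The protocol's Statistical Analysis Plan lists Friedman's "test for comparison between methods" without naming the variable. The SAP supplies it: Friedman's "test was used to compare between number of canals detected by the three methods".
- **Kappa.** Both documents use it for agreement between methods.
- **Correct versus incorrect cases.** The SAP compares these by t-test or Mann-Whitney, then adds a model: "Binary logistic regression model was constructed using diagnosis (Correct/Incorrect) as the dependent variable". Its covariates are listed in full: "Treatment, molar type, inter-orifice distance, percentage of canal unity and Vertucci classification were the independent variables". Neither document says what makes a diagnosis correct.
- **ROC.** The SAP describes a curve for the "diagnostic accuracy measures of AI in relation to CBCT" and adds: "Comparison between areas under the ROC curve (AUC) were performed using z-test". The protocol mentions an AUC comparison with no further detail.

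**The concern.** Superior accuracy means being right more often against a known truth. Friedman's test on counts involves no truth: a false canal raises a method's rank exactly as a true one does. The test detects a shift in counts and says nothing about whether the shift is towards or away from the correct number.

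The analysis that does concern accuracy, the ROC, is left open where it matters. The AUCs are not identified, the only other method named is CBCT (itself a comparator in the hypothesis), and clinical examination does not appear. A significant Friedman result could therefore be reported as superior accuracy when it shows only that AI counts more canals.

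**Working it through.** **1. Can any planned analysis test the hypothesis?**

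| Analysis | What it uses | Tests AI's accuracy against both comparators? |
|---|---|---|
| Friedman | Counts, no reference | No: count shift |
| Kappa | Counts, no reference | No: agreement |
| t-test, Mann-Whitney | Correct/incorrect by case feature | No: methods not compared |
| Logistic model | Correct/incorrect, five covariates | No: method is not a covariate |
| ROC and z-test | AI and CBCT; AUCs unnamed | Not shown; clinical examination absent |

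**2. The reference.** A method scored against itself is right in 212/212 = 100% of teeth. With CBCT as reference, AI can at most equal CBCT; with DOM as reference, AI can at most equal clinical examination. Superiority over both therefore needs a third reference, and neither document describes one. The Results paragraph of the protocol's opening summary does not settle this. It treats the clinical count as truth in one five-canal tooth, yet ranks AI above clinical examination overall.

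**3. Inputs for the illustration.** 212 molars (protocol, Study Design); AI accuracy 88.2% (protocol, opening Results); significance level 0.05 (SAP). The numerator is inferred: 187/212 = 88.2%, whereas 185/210 = 88.1% and 186/210 = 88.6%. Everything else below is assumed.

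**4. Formulas.** Let d be the rank of a method within a tooth minus the mean rank 2, and D the sum of d over teeth for that method. Tie-corrected Friedman with k = 3 is Q = (k - 1) × ΣD² / Σd², with P = exp(-Q/2) on 2 df. Exact McNemar with all m discordant teeth on one side gives P = 2 × 0.5^m. The paired difference δ has 95% CI δ ± 1.96 × √((ψ - δ²)/n), where ψ is the proportion of discordant teeth.

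**5. Same Friedman result, opposite accuracy.** In 25 teeth the counts are AI 4, CBCT 3, DOM 3. The other 187 teeth agree and are correct.

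- Each of the 25 teeth has d = +1, -0.5, -0.5, so Σd² = 25 × 1.5 = 37.5.
- D = +25, -12.5, -12.5, so ΣD² = 625 + 156.25 + 156.25 = 937.5.
- Q = 2 × 937.5/37.5 = 50.0; P = exp(-25) = 1.4e-11.
- If the 25 extra canals are false, AI is 187/212 = 88.2% and the others 100%. If they are true, AI is 100% and the others 88.2%.
- McNemar gives 2 × 0.5^25 = 6.0e-8 in both cases, in opposite directions. The difference is 25/212 = 11.8 points, 95% CI 7.5 to 16.1 in size.

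**6. Null Friedman result, AI more accurate.** AI is correct in 187/212 and each comparator in 163/212 (76.9%, assumed). Missed and added canals balance to within one tooth. The difference is 24/212 = 11.3 points.

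| Overlap of errors | Friedman | Discordant teeth | Exact McNemar | 95% CI (points) |
|---|---|---|---|---|
| None shared | Q = 0, P = 1 | 49 v 25 | P = 0.0071 | 3.5 to 19.1 |
| All AI errors shared | Q = 0, P = 1 | 24 v 0 | P = 1.2e-7 | 7.1 to 15.6 |

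**7. Simulation** (4,000 runs, 212 molars, true count 3 or 4 equally likely, independent one-canal errors).

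| Assumed accuracy and errors | Friedman P ≤ 0.05 | Cochran's Q P ≤ 0.05 |
|---|---|---|
| All 88.2%; AI over-counts, others under-count | 100% | 5.5% |
| AI 88.2%, others 75%; symmetric errors | 5.3% | 96.8% |
| AI 75% (over-counts), others 88.2% (symmetric) | 100% | 96.6% |

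A second simulation let errors correlate between methods (latent correlation 0 to 0.8), because AI and the CBCT readers use the same scans. Accuracies were AI 88.2%, CBCT 78% and DOM 75%. Friedman was significant in about 5% of runs when half the errors were missed canals, 47-80% when four fifths were, and 92-100% when all were. McNemar favoured AI over CBCT in 77-98% of runs and over DOM in 93-100%, across all shares.

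**The case against.** The strongest reply is that the plan never assigns the accuracy hypothesis to Friedman. The SAP says plainly that it compares counts, which is a legitimate use, and the protocol gives accuracy to the ROC analysis. That is fair, and it places the main fault in the undefined reference and unnamed AUCs. It does not rescue the plan, because the ROC is then the only candidate test, and it is not specified and omits one comparator.

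Second, the null-Friedman example does not resemble the study as summarised. The protocol's opening Results report that AI found significantly more molars with three or four canals in conventional cases (P < 0.001). This stands: step 6 shows a general property of the test, not something seen here. Where nearly all errors are missed canals, Friedman's loss of power also disappears. Step 5 is unaffected, since a count shift is exactly what it assumes, and the documents do not say whether the extra canals were real.

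Third, the opening summary mentions sensitivity and specificity, and it compares AI accuracy between molar types, which may be what the z-test is for. The first also needs a reference that is not given; the second would not compare methods.

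Finally, the five-canal tooth is one case and does not contradict higher overall accuracy for AI. It shows only that the reference is unsettled.

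**Conclusion.** The concern holds and must be fixed. As written, the plan specifies no valid test of AI's superior accuracy over either comparator, and the gap is wider for clinical examination. This follows from the documents' wording and needs no numerical assumption.

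The figures show the possible size of the error. An identical Friedman result (Q = 50.0) fits AI being 11.8 points worse or 11.8 points better than each comparator. They rest on constructed tables with 212 molars; only the 88.2% comes from the documents, and the comparator accuracies and error directions are assumed. No accuracy conclusion can rest on the Friedman test.

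**What to change.** Amend the SAP as follows.

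1. Name the reference that defines a correct diagnosis, and state which AUCs the z-test compares, against which reference and for what target condition. CBCT cannot be the reference where AI is compared with CBCT.
2. Score each tooth correct or incorrect for each method and make a paired comparison the between-method accuracy test.
   - **DOM as reference:** exact McNemar for AI versus CBCT, with the paired difference and 95% CI. Drop the claim of superiority over clinical examination.
   - **CBCT as reference:** superiority over CBCT cannot be tested. AI and DOM could formally be scored against it, but AI and the CBCT readers share the same scans, so the comparison may favour AI; the SAP would have to say so.
   - **Reference independent of all three:** McNemar for AI against each comparator, preceded by Cochran's Q if an overall test is wanted, or a paired comparison of named AUCs.
3. Keep Friedman as a description of count shift and draw no accuracy conclusion from it.

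The cost is SAP wording and a short re-analysis of counts already recorded. With DOM as reference, the price is a narrower conclusion. An unbiased test against clinical examination needs a reference the documents do not describe, so that claim needs new data or has to go.

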**Title:** Diagnostic Accuracy of Artificial Intelligence, CBCT, and Clinical Examination in Detecting Number of Root Canals in Conventional and Retreated Maxillary and Mandibular Molars

NCT Number: "Pending"

Date: 29/10/2024

Introduction: Accurate root canal detection is crucial for successful endodontic treatment, particularly in complex molar cases. Conventional methods, such as clinical examination and cone-beam computed tomography (CBCT), have their limitations, as high radiation exposure. Recent advancements in Artificial Intelligence (AI) have shown promise in improving diagnostic accuracy. This study aims to compare the effectiveness of AI, CBCT, and clinical examination using a dental operating microscope (DOM) in detecting root canals in upper first, upper second, and lower first molars, in both conventional and retreatment cases.

Methods: CBCT scans from 210 patients requiring non-surgical root canal therapy or re-treatment were selected. The scans were analyzed using three detection methods: clinical examination via DOM, interpretation by two experienced endodontists using CBCT, and an AI convolutional neural network (CNN) software (Diagnocat). The detected number of root canals was recorded and compared across the three methods. Statistical analysis was performed to evaluate the diagnostic accuracy, including sensitivity, specificity, and agreement between methods.

Results: AI detected a significantly higher number of molars with three or four canals compared to clinical examination and CBCT in conventional treatment cases (P < 0.001). In retreatment cases, AI demonstrated a similar trend, with one case of five root canals detected clinically but missed by both CBCT and AI. Overall, AI showed higher diagnostic accuracy (88.2%) compared to clinical examination and CBCT. There was no significant difference in AI accuracy between molar types, though the upper first molar had the highest accuracy (93.9%).

Conclusion: AI demonstrated higher accuracy in detecting root canals compared to CBCT and clinical examination in both conventional and retreatment cases, particularly in upper molars. These findings highlight the potential of AI as a valuable tool for enhancing diagnostic precision in endodontics, especially in complex cases. However, further research is necessary to address the limitations of AI

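### Friedman's test is the only planned comparison of canal counts and no pairwise test follows it, so it cannot support a statement that AI is higher than both CBCT and clinical examination

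*SAP*

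**What the plan says.** The SAP gives one test of canal numbers across the three methods: Friedman's "test was used to compare between number of canals detected by the three methods". The Protocol's Statistical Analysis Plan section lists the same item, "Friedman's test for comparison between methods". On the threshold, the SAP states "The significance level was set at" P ≤ 0.05. Neither document names a post-hoc test, a pairwise test or a rule for multiple comparisons.

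Two other items compare methods. One is "Kappa statistics for agreement between methods". The other is a ROC analysis in which the SAP evaluates AI against CBCT and then compares areas under the curve by a z-test, without saying which areas.

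The Protocol's hypothesis names two comparators: "AI will demonstrate superior diagnostic accuracy compared to CBCT and clinical examination". The Results paragraph of its opening abstract says "AI detected a significantly higher number of molars with three or four canals compared to clinical examination and CBCT in conventional treatment cases", with a single P < 0.001. For retreatment cases the abstract speaks of a similar trend and gives no P value.

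**The concern.** With three methods, Friedman's test has one null hypothesis: all three give the same distribution of counts. Rejecting it says only that this is untrue somewhere. If the microscope finds fewer canals than either reading of the scan, the test will reject even when AI and CBCT are interchangeable. Someone following the plan then has a significant P value and three rank sums, and nothing that separates AI from CBCT. If AI happens to rank first, the natural sentence is that AI was significantly higher than both.

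A very small P value gives no protection, because it can arise entirely from the microscope. At stake is the AI-versus-CBCT half of the abstract's count result in conventional cases.

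**Working it through.** **Inputs from the documents.** Three methods on the same teeth, so Friedman's test has 3 − 1 = 2 degrees of freedom. Threshold 0.05. Sample size 212 molars (Protocol, Study Design). Stratum sizes, miss rates and power are not given, so there is no figure of the plan's own to reproduce.

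**Assumptions.** The true count is 3 or 4 with equal probability. AI and CBCT have identical errors: one canal too many and one too few, each with probability 3% or 6%. The microscope has the same rate of overcounting but misses one canal with probability 10% to 30%. A treatment stratum of half the sample is taken as 212 / 2 = 106. Each setting has 4,000 simulated studies, so the Monte Carlo standard error is at most √(0.25 / 4,000) = 0.8 points. The tie-corrected Friedman statistic was checked against a standard library routine.

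**Expected size.** If AI and CBCT are exchangeable, AI ranks above CBCT in about half of the significant results, slightly less because of ties:

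P(false AI > CBCT reading) ≈ ½ × P(Friedman significant).

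**Results, n = 212.**

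| AI and CBCT error, each way | Microscope miss rate | Friedman significant | Half of that | Significant and AI above CBCT | Same, with exact paired sign test added |
|---|---|---|---|---|---|
| 3% | 3% (all equal) | 5% | 2% | 2% | 1.0% |
| 3% | 10% | 70% | 35% | 35% | 1.2% |
| 3% | 15% | 98% | 49% | 48% | 1.5% |
| 3% | 20% | 100% | 50% | 48% | 1.4% |
| 3% | 30% | 100% | 50% | 49% | 1.5% |
| 6% | 6% (all equal) | 5% | 3% | 3% | 1.0% |
| 6% | 10% | 19% | 9% | 9% | 1.2% |
| 6% | 15% | 67% | 34% | 33% | 1.7% |
| 6% | 20% | 95% | 47% | 46% | 2.0% |
| 6% | 30% | 100% | 50% | 49% | 1.9% |

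**Results, n = 106.** The false reading occurs in 20% to 48% of studies with 3% errors and in 5% to 48% with 6% errors. With the exact sign test added it is 0.9% to 1.3%. Over both sample sizes, an uncorrected McNemar-type test in its place gives 1.5% to 3.1%.

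**A second model.** AI and CBCT each record four canals in 50% of teeth, the microscope in 35% or 40%, with correlated readings. AI is strictly highest with a significant Friedman test in 21% to 48% of studies. Adding Holm-adjusted paired tests leaves a false AI > CBCT claim in 1.2% to 2.2%.

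**How much adjustment is needed.** With three methods there are three pairwise hypotheses, and any two of them together imply that all three methods are equal. Testing that global hypothesis by Friedman at 0.05, and then each pair at 0.05, is therefore a closed procedure that controls the family-wise error within a stratum. Two strata each run at 0.05 give 1 − 0.95² = 9.75%, so adjustment matters across strata.

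**Does the AUC comparison help?** If CBCT supplies the reference classification, it agrees with itself by construction, and every canal that AI reports beyond CBCT counts as an AI error. That analysis cannot show AI to be better than CBCT. Kappa measures agreement and has no direction. The t-tests, Mann-Whitney tests and logistic regression compare correctly with incorrectly diagnosed cases, not one method with another.

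**The case against.** The strongest reply has four parts.

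- **The plan does compare accuracy.** The hypothesis concerns accuracy, and the AUC z-test is the tool for it, so Friedman need not carry the claim. It is true that Friedman is not the only between-method statistic, and that a test of counts does not test the accuracy hypothesis. The AUC test still cannot settle AI against CBCT, for the reason shown above, and the abstract's statement is about counts.
- **The abstract names no test.** Pairwise tests may have been run and left undescribed. That possibility stands, and is why the source of P < 0.001 is given here as an inference.
- **The rates are assumed.** This stands. Where the microscope is only slightly worse (10% against 6%), the false reading falls to 5% to 9%, and if all three methods are equal it is about 2%. The ceiling near 50% needs only that AI and CBCT be exchangeable and the microscope clearly different.
- **Multiplicity is easily exaggerated.** A reader might count three pairs in two strata and infer a family-wise error of 1 − 0.95⁶ = 26%. The documents do not support that: they plan no such six tests, the three contrasts share methods and are not independent, and a preceding Friedman test restrains them. The defect is a missing pairwise test.

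**Conclusion.** The point holds for counts. As written, the plan supplies an omnibus test, while the abstract makes a statement about two specific pairs. If AI and CBCT are equal and the microscope finds clearly fewer canals, the false reading that AI is highest arises in roughly 20% to 50% of studies; a paired test brings this to about 1% to 2%. These figures illustrate the mechanism under assumed rates and do not estimate the error in this study.

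A reader might go further and infer that AI did not in fact exceed CBCT. The documents give no counts by method, so they cannot show that; they show only that the listed test does not establish it. Nor is a second significance claim made for retreatment, where the abstract gives no P value. The correction is worth making because the statement is prominent and the paired data already exist.

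**What to change.** Add to the SAP, and apply to the existing data:

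- Run Friedman's test separately in conventional and retreatment cases. Where it is significant, compare AI with CBCT and AI with clinical examination on the same teeth, by Wilcoxon signed-rank or exact sign test, or by exact McNemar test if counts are split at a stated cut. State whether tests are two-sided.
- Report each paired difference with its 95% confidence interval.
- If both strata are to support claims, adjust across them, for example by working at 0.025 in each. Further adjustment within a stratum is optional.
- Say that AI detects more canals than a comparator only for pairs that pass, and confine that statement to counts. It is not evidence of higher accuracy.
- State which test produced P < 0.001, and which AUCs the z-test compares.
- Label the paired tests post hoc. The SAP is written in the past tense and the Protocol already reports results, so they cannot now be called prespecified.

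The cost is a few sentences, a few extra tests on data in hand, and slightly larger P values where the adjustment across strata is used.

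### The protocol and SAP were written with the data in view, so prespecification of the AI superiority hypothesis and its 0.05 tests cannot be verified

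*SAP*

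**What the plan says.** Both documents carry the line "Date: 29/10/2024" and a registry number that is still pending.

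The protocol opens with an abstract whose Methods are in the past tense and which has Results and a Conclusion. It reports that AI found significantly more molars with three or four canals "compared to clinical examination and CBCT in conventional treatment cases (P < 0.001"), that in retreatment cases "AI demonstrated a similar trend, with one case of five root canals detected clinically but missed by both CBCT and AI", and that "Overall, AI showed higher diagnostic accuracy (88.2%) compared to clinical examination and CBCT". It gives 93.9% for the upper first molar and concludes that AI was the more accurate method.

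Later sections of the protocol look forward. Study Objectives and Hypotheses says "AI will demonstrate superior diagnostic accuracy compared to CBCT and clinical examination". Study Timeline lists "Participant recruitment (2 months") and then three months for analysis and reporting. The section headed Statistical Analysis Plan has four items: frequencies and percentages, Friedman's test, "Kappa statistics for agreement between methods", and ROC analysis with comparison of AUCs.

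The SAP is one paragraph in the past tense. It reports that "All data showed normal (parametric) distribution except for length of canal division from the apex and percentage of canal unity data" and assigns Student's t-test or Mann-Whitney accordingly. It adds a logistic model for correct versus incorrect diagnosis with five independent variables, and sets significance at P ≤ 0.05.

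**The concern.** A 0.05 error rate keeps its usual meaning only if the hypothesis, the outcome and the test were fixed before anyone looked at the data. A protocol and SAP are normally the evidence for that. Here the document that states the hypothesis also reports results in the same direction, and the document that names the tests also reports what the data looked like. At stake is whether the finding that AI outperforms CBCT and clinical examination can be read as a confirmed hypothesis, or only as an observation that needs confirmation in other data.

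**Working it through.** **1. When was the text written?** Statements under the one date, side by side:

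| Place | Content | Could it be written before the data were seen? |
|---|---|---|
| Protocol, abstract Results and Conclusion | P < 0.001; 88.2%; 93.9%; AI more accurate | No |
| SAP | Which variables proved normal and which did not | No |
| Protocol, Study Objectives and Hypotheses | AI superiority, future tense | Yes |
| Protocol, Study Timeline | Recruitment and analysis as milestones, no calendar dates | Yes |

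The first two rows settle that both documents, as they stand, post-date at least part of the analysis. The last two are why the protocol can be taken for a prospective plan.

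**2. Is there evidence of an earlier plan?** Ethical Considerations records IRB approval but gives no date. The available text gives no dates of data collection or analysis and refers to no pre-data version. The sample size of 212 molars has no justification, and no primary outcome or primary test is named.

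**3. How far does the normality finding reach?** In the SAP it decides only between the t-test and Mann-Whitney for correctly versus incorrectly diagnosed cases. Friedman, kappa and ROC/AUC appear in both documents, and neither says that they were chosen from the data.

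**4. How do the two analysis lists compare?** Descriptive statistics, Friedman, kappa and ROC/AUC are in both. The t-test, Mann-Whitney test and logistic model are in the SAP only.

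**5. Arithmetic check on the reported accuracy.** The inputs are 88.2% (abstract), 210 patients (abstract) and 212 molars (Study Design). It is assumed that overall accuracy uses all units as its denominator.

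- Out of 212: 187/212 = 88.21%, which rounds to 88.2%.
- Out of 210: 185/210 = 88.10% and 186/210 = 88.57%. No whole number of patients gives 88.2%.

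So the reported accuracy fits the 212 molars listed as the sample size. This is consistent with 212 being the analysed count, but a planned target that was met exactly would give the same result. It is supporting detail only.

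**The case against.** The best defence is that the documents show when the text was written, not when the hypothesis and tests were chosen. An IRB reviewed the study, its version may predate the data, and a hypothesis that agrees with the result may simply have been borne out. This stands. A reader might infer that the superiority hypothesis was written to fit the results; nothing in the documents establishes that.

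Three further limits also stand.

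- A reader might infer that the data-driven test choice undermines the comparison of AI with CBCT and clinical examination. Step 3 shows that it does not reach those tests.
- A reader might say that both documents pose as prospective. Only the protocol has forward-looking sections; the SAP is openly retrospective and holds no accuracy figures or test P values. The protocol's Conclusion also calls for further research.
- A reader might try to size the problem as multiplicity. One count is 2 Friedman tests (one per treatment group), 3 numerical comparisons (an assumed number, which the SAP does not give), 5 model terms and 1 to 3 AUC comparisons, so 11 to 13. But 3 + 5 = 8 of these compare correct with incorrect diagnoses and cannot produce a false finding that AI is superior. A P value below 0.001 stays below 13 × 0.001 = 0.013 after Bonferroni over 13 tests. Multiplicity is therefore not the measure of this problem.

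Nor are the SAP's additional analyses all without an aim. The protocol's Introduction covers molar type and both conventional and retreatment cases, and two of the five model terms match that. Only the anatomical terms lack a stated objective.

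None of this supplies the missing evidence that hypothesis, outcome and test were fixed first.

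**Conclusion.** The point holds in this form: both documents were written with knowledge of the data, so they cannot serve as evidence of prespecification, and the P values cannot carry a confirmatory superiority claim. The firmer statement, that the hypothesis and tests are post hoc, goes beyond the documents.

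The size is one of status, not of number. The reported 88.2%, 93.9% and P < 0.001 are not shown to be wrong, but they rank as exploratory unless a pre-data plan is produced. The conclusion assumes that no such version exists beyond the text reviewed here. If one does, and it contains the hypothesis and the between-method tests, most of the concern falls away. What would remain is the disclosure, and the labelling of any SAP analyses which that version does not contain.

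**What to change.** 1. State at the head of both documents that they were finalised after the data were analysed, and give the dates of data collection, analysis and IRB approval.
2. Supply any version that predates the data and contains the hypothesis and tests.
3. If there is none, keep the hypothesis visible, since rewriting it now would obscure the record. Label it and all analyses exploratory, call the P values nominal, and reword the Conclusion as hypothesis-generating.
4. Mark the t-tests, Mann-Whitney tests and logistic model as not in the protocol's analysis list, without asserting when they were chosen, and disclose any analysis that was run but not reported.

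The cost is wording in both documents and a weaker headline claim. No new data are needed.

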## **Study Design**

- Sample Size: 212 molars.
- Randomization: Not applicable (observational study).
- **Blinding**: Independent assessment by two experienced endodontists for CBCT and clinical examination.
- Control Group: Not applicable.

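### Student's t-test for correct versus incorrect teeth assumes equal variances that are never checked; at a probable split of about 187 to 25, Welch's test is the safer choice

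*SAP*

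**What the plan says.** The SAP's Statistical Analysis section examines numerical data "using tests of normality (Kolmogorov-Smirnov and Shapiro-Wilk tests"). It then reports that "All data showed normal (parametric) distribution except for length of canal division from the apex and percentage of canal unity data". Measures that pass go to Student's t-test: "t-test was used to compare between correctly and incorrectly" diagnosed cases. The two that fail go to the Mann-Whitney U test for the same comparison. "The significance level was set at" P ≤ 0.05.

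The section mentions no variance check and no unequal-variance version of the t-test. It also plans a binary logistic regression of correct versus incorrect diagnosis, with inter-orifice distance among the predictors. The protocol's own Statistical Analysis Plan section does not list the t-test.

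The group sizes are not stated. The inputs for them are in the protocol: "Sample Size: 212 molars" under Study Design, and, in the Results paragraph of the opening summary, "Overall, AI showed higher diagnostic accuracy (88.2%) compared to clinical examination and CBCT".

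**The concern.** By name, Student's t-test is the pooled test, which assumes that the two groups share one variance. A normality test says nothing about that assumption.

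With equal group sizes the omission would hardly matter. With very unequal sizes it can, because the pooled SD is then set almost entirely by the larger group, while the uncertainty of the mean difference comes mostly from the smaller one. If the incorrectly diagnosed teeth are more variable than the others, the standard error is too small and false differences appear too often. If they are less variable, the standard error is too large and real differences are missed.

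At stake is whether a measure such as inter-orifice distance is reported as differing between teeth that were diagnosed correctly and teeth that were not.

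**Working it through.** **Inputs**
- Teeth: 212 (protocol, Study Design).
- Proportion correct: 88.2% (protocol, opening summary, Results). Taking this as the SAP's correct/incorrect split is an assumption.
- Level: 0.05 (SAP), assumed two-sided because sidedness is not stated.
- SDs: not given. The SD ratio r = SD(incorrect)/SD(correct) is therefore varied as an assumption.

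**Step 1: the split.** 212 × 0.882 = 186.98, so 187 correct and 212 − 187 = 25 incorrect. Check: 187/212 = 88.21%. The summary also says "CBCT scans from 210 patients requiring non-surgical root canal therapy or re-treatment were selected", but 210 does not fit as the denominator: 185/210 = 88.1% and 186/210 = 88.6%. The ratio is 187/25 ≈ 7.5 to 1.

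**Step 2: formula.** Let n₁ = 187 and n₂ = 25, and set SD(correct) to 1. In large samples the true level of the pooled test is

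α = 2 × [1 − Φ(t_crit × k)], with k = √{ s_p² (1/n₁ + 1/n₂) / (1/n₁ + r²/n₂) }, s_p² = (186 + 24r²)/210 and t_crit = 1.971 on 210 df.

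**Step 3: two worked values.** Here 1/187 + 1/25 = 0.04535.
- r = 1.5: s_p² = (186 + 54)/210 = 1.1429. The denominator is 0.00535 + 2.25/25 = 0.09535. k = √(1.1429 × 0.04535 / 0.09535) = 0.737. t_crit × k = 1.453, so α = 14.6%.
- r = 0.8: s_p² = (186 + 15.36)/210 = 0.9589. The denominator is 0.00535 + 0.64/25 = 0.03095. k = √(0.9589 × 0.04535 / 0.03095) = 1.185. t_crit × k = 2.337, so α = 2.0%.

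**Step 4: simulation.** Normal data, equal means, 187 versus 25, 200,000 data sets per ratio. The plan's own figure comes first: at r = 1 Student's test gives 5.0%, so the stated level is reproduced when the variances are equal.

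| SD ratio r | Variance ratio | Student, formula | Student, simulated |
|---|---|---|---|
| 0.67 | 0.45 | 0.8% | 0.8% |
| 0.8 | 0.64 | 2.0% | 2.0% |
| 0.9 | 0.81 | 3.3% | 3.4% |
| 1.0 | 1.00 | 4.9% | 5.0% |
| 1.1 | 1.21 | 6.7% | 6.8% |
| 1.25 | 1.56 | 9.6% | 9.8% |
| 1.5 | 2.25 | 14.6% | 14.7% |

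Welch's test gives 5.0% to 5.1% at every ratio. Separate smaller simulations differ from the table by only 0.1 or 0.2 percentage points.

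**Step 5: what drives it.** With 106 versus 106 teeth, Student's test stays at about 5.0% at every ratio, so the imbalance is the cause. Total size matters little: at 60 versus 8, nearly the same imbalance, r = 1.5 gives 14.6%.

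**Step 6: price of Welch.** With equal variances and a true difference of 0.6 SD, power is about 80% for Student's test and 78% for Welch's.

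**The case against.** **No SDs are given.** This stands. Every figure away from 5% rests on an assumed SD ratio, and at a 10% difference in SD the distortion is mild. A reader might infer that the reported P values are already wrong, or that any small variance difference ruins the test. The documents support neither. A rate above 20% would need an SD ratio of about 2, a fourfold difference in variance, and nothing in the documents suggests one.

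**The split is inferred.** This also stands. The SAP does not say that a correct diagnosis means correct by AI, or that every tooth has every measurement. A less unbalanced subset would shrink the effect: at 170 versus 42, r = 1.5 gives 12.2%.

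**The analyst may have read the unequal-variance row.** SPSS prints both rows, and the name Student's t-test may be loose wording. If the row was chosen by Levene's test, the level would be about 7.4% at r = 1.25, 6.9% at 1.5, 3.6% at 0.8 and 4.5% at 0.67. That removes much of the harm, but the SAP states no such step. Levene's test would also detect r = 1.25 only about 30% of the time at this split.

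**The scope is narrow.** This stands. The SAP names three numerical measures, and two go to Mann-Whitney. Only inter-orifice distance is left, and the logistic regression, which does not assume equal variances, covers it as well. A reader might infer that these t-tests are the plan's account of why AI errs. The documents do not say so, and the regression is the natural place for that question.

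**Mann-Whitney is not immune.** True: under unequal spread with equal centres, its rejection rate at this split is about 9% at r = 1.5. The normality result is also the only basis for sending those two measures there. Asking to abolish the normality check while keeping its allocation would be inconsistent, so this point asks only for a change to the t-test.

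**Conclusion.** The point holds as a cheap improvement to a secondary analysis. The SAP names a test whose level depends on equal variances, reports no check of them, and probably applies it at about 7.5 to 1. If the incorrect group's SD is 25% to 50% larger, the true level is about 10% to 15%. If the ratio is 0.8 to 0.67, it is about 2% to 0.8%, with power lost. Within 10% either way, it is about 3.4% to 6.8%.

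This rests on four assumptions: normal data, a two-sided test, the pooled form that the name implies, and a split of about 187 to 25.

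A reader might go further and doubt the comparison of AI, CBCT and clinical examination. The documents do not support that. Those comparisons use Friedman's test, kappa and ROC analysis, and no result in the protocol's summary rests on the t-test.

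**What to change.** In the SAP's Statistical Analysis section, name Welch's unequal-variance t-test in place of Student's for the measures now sent to the t-test. Report the mean difference with its 95% CI, taken from the unequal-variance row of the SPSS output. Leave the Mann-Whitney tests for the two named measures as they are. It would also help to state whose diagnosis defines correct and incorrect, and the number of teeth in each group for each measure.

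The cost is one line in the SAP. The SAP is written in the past tense; if the analysis is already done, the figures come from the same SPSS output and no new data are needed. The downside is about 2 points of power if the variances are in fact equal.
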